Protocol Title: Use of a hyperinsulinemic-hypoglycemic clamp to study hypoglycemia: a method development study.

PI Name: [name]

Sub-Investigator's Name(s): [name], [name], and [name].

Protocol Version Date: November 15th, 2018

Funding: LA CATS/Internal

Objectives

Hypoglycemic complications are a major impediment to the maintenance of healthy glucose levels in persons with diabetes. We recently completed a clinical pilot and feasibility study (GLIMPSE), which identified a novel biomarker that appears to predict the susceptibility to hypoglycemia [1]. By providing an assay to predict hypoglycemic events and therefore diabetic complications, the development of this biomarker could significantly improve the treatment of persons with diabetes.

To pursue such line of research requires the induction and maintenance of hypoglycemia in a controlled safe clinical research setting. A hyperinsulinemic-hypoglycemic clamp is an experimental procedure, which allows for hypoglycemia to be studied in a safe and controlled manner [e.g. 2, 3]. The goal of this study is to establish the hyperinsulinemic-hypoglycemic clamp procedure at Pennington Biomedical Research Center in order to apply the knowledge gained to future studies which will determine the efficacy of our biomarker for predicting susceptibility to hypoglycemia [e.g. aim 2 of the PI's recently funded LA CaTS Roadmap Scholars grant (see appendix A below for project specific aims)]. Additionally, our use of continuous glucose monitoring (CGM) during the clamp procedure will provide novel data regarding the accuracy of CGM during hypoglycemic conditions in a controlled research setting.

Given that the primary purpose of this study is for method development, there is no hypothesis being tested or statistical comparison being made across study participants. We will analyze the time course of the changes in our endpoints in each subject to verify that our procedure produces results that are similar to previously published data from other institutions which have used the hypoglycemic clamp technique. This will allow us to develop an institutional MOP for the hypoglycemic clamp which can be used to safely implement this technique in future studies.

Background

Although Pennington Biomedical has extensive experience with euglycemic clamp procedures since its introduction by [name] [e.g. 4, 5], experience performing the hypoglycemic clamp procedure is lacking. The procedural differences between the euglycemic clamp and hypoglycemic clamp are minimal. For example, both procedures involve the paired infusion of insulin and glucose, with the rate of glucose infusion being adjusted to achieve a targeted steady-state blood glucose level. In most instances, the

rate of insulin infusion is identical between the two procedures, whereas the rate of glucose infusion differs due to the difference in the targeted blood glucose concentration, which is approximately 100 mg/dL for the euglycemic clamp and 50 mg/dL in the hypoglycemic clamp. Therefore, in order to achieve the lower steady state blood glucose, the initial rate of dextrose infusion during the first 45 minutes of the procedure will be significantly less than the typical rate of dextrose infusion during a euglycemic clamp.

Given our considerable experience with euglycemic clamp and the similarities between the two procedures, we do not anticipate any issues preventing successful implementation of the hypoglycemic clamp procedure. In addition, we have consulted with [name] from the University of Minnesota who has directed multiple studies which utilize this procedure [e.g. 2, 6], to develop the procedure at Pennington (see attached letter of support).

Study Participants

We will enroll up to 8 healthy men or women (goal n=3 completers) in this method development study.

Inclusion and Exclusion Criteria

Inclusion Criteria:

- Healthy male or female
- Ages 18-40 years
- BMI between 20 kg/m² and 30 kg/m² (± 0.5 kg/m² will be accepted)
- Medically cleared for participation in the study

Exclusion Criteria:

- History of clinically diagnosed diabetes or a fasting blood glucose >126 mg/dL
- Average screening blood pressure >140/90 mmHg
- History of cardiovascular disease
- Pregnant, planning to become pregnant, or breastfeeding
- Based on the investigative team's clinical judgement, a subject may not be appropriate for participation in the study.

If eligible, individuals will be enrolled and undergo all testing procedures.

Recruitment Methods

Potential participants will be recruited through PBRC via IRB approved recruitment materials (e.g., landing page, listserv, social media). Individuals can either complete the webscreening form directly from the PBRC landing page, call PBRC directly, or e-mail the Recruitment Core. Potentially eligible participants will then undergo a phone screen to answer a series of yes or no questions regarding eligibility. Eligible individuals will be scheduled for a screening visit at PBRC.

Study Timelines

A participant's duration of study participation will be 3 days. The estimated duration to enroll all study subjects is anticipated to be four months. The estimated duration to complete the study is 6 months.

Study Endpoints

Primary endpoints:

- Blood glucose levels

Secondary endpoints:

- Serum epinephrine, norepinephrine, glucagon, and cortisol.
- CGM glucose

The overarching goal of measuring these endpoints is to demonstrate our ability to safely perform hypoglycemic clamps, while simultaneously developing a systematic set of procedures (MOP) which will ensure a high rate of success and reliability in future studies utilizing this procedure.

Procedures

Participants will complete a screening visit, and one study visit conducted in the PBRC Inpatient Unit. See Table 1 for schedule of assessments.

Table 1. Schedule of Clinic Assessments

	Screening Visit	Run-in Visit (2-3 days prior to Study Visit)	Study Visit
Procedures			
Informed Consent	X		
Metabolic Weight, Height*, BMI	X		X
Vital Signs (blood pressure, heart rate)	X		X
Fasting Blood Draw (CBC and Chem 14)	X		
Screening Health Questionnaire	X		
Medical History	X		
Physical exam	X		
Run-in meal		X [‡]	
CGM sensor placement		X	
Pregnancy test (urine)			X
Hyperinsulinemic hypoglycemic clamp [†]			X
Continuous glucose monitoring			X
Meal (lunch)			X

*Height will only be measured during the Screening Visit

[‡]Meal will be consumed the night before study visit. Participant will pick up their meal up to 2-3 days prior to Study Visit.

[†]IV procedure and serial blood collection

CGM: Continuous glucose monitoring

Screening Visit:

Participants will complete a screening visit at the Pennington Biomedical Outpatient Clinic to assess eligibility. Participants will arrive in the morning to the PBRC Outpatient Unit, and after providing written informed consent, the following procedures will be completed: anthropometrics, vital signs, fasting blood draw (CBC and Chem 14), screening health questionnaire, and medical history and physical examination by one of the medical staff members. The study PI, [name], will conduct a final review of the participants' charts to determine eligibility.

Run-in Visit:

2-3 days prior to the study Visit, participants will be scheduled for a run-in visit to pick up their meal and a continuous glucose monitor (CGM) sensor will be placed on their abdomen.

Study Visit:

Eligible subjects will be scheduled for the Study Visit which will last approximately 8 hours. Participants will be provided a run-in meal (supper) which will be consumed the evening before their visit. Participants will be instructed to 1) eat nothing but the meal provided after 3 PM, 2) eat the entire meal before 9 PM, and 3) drink only water after 3 PM. Participants will be instructed to pick up their meal within 3 days prior to their study visit.

Subjects will arrive at the inpatient unit in the morning after at least a 10 hour overnight fast. Upon arrival to PBRC, participants will be admitted to the inpatient unit. Following measurement of metabolic weight, vitals, and pregnancy test (women only), the 4-hour hypoglycemic clamp procedure (30 minute baseline, 120 minute insulin infusion, and 90 minute recovery) will be performed. Upon completion of the clamp procedure, participants will be provided lunch (Standard American Diet). Following lunch, the CGM sensor will be removed and pending a stable blood glucose level in the normal range, the participant will be discharged from the inpatient unit. This completes the study.

Study Procedure Descriptions

- Anthropometrics: Fasting body metabolic weight will be collected with participants wearing a hospital gown and underwear. Height will be collected once at screening.
- Blood collection (study use): Approximately 7.5 mL of whole blood will be collected during the screening visit. Approximately 120 mL of whole blood will be collected during the hypoglycemic clamp procedure for measurement of glucose, potassium, and counter-regulatory hormones. The total volume of blood that will be collected during the study is approximately 128 mL.
- Continuous glucose monitoring: Blood glucose will be assessed using continuous glucose monitoring (CGM). Briefly, the abdominal area will be disinfected, and then trained staff from the Inpatient Unit will insert a glucose sensor under the skin

in the abdominal area. The sensor has a small needle-like probe that inserts into the subcutaneous fat of the abdomen and measures blood glucose levels without removing blood from the body. The sensor will then be attached to the recording unit, and the set-up will be secured with adhesive to the participant's body. After an initial period of equilibration with interstitial glucose, the sensor will be calibrated via the blood glucose measurement obtained during the hypoglycemic clamp procedure. The CGM device records interstitial glucose every 5 minutes and will allow a more complete profile of blood glucose changes during the study visit.

- Hyperinsulinemic-hypoglycemic clamp: An intravenous catheter will be placed in an antecubital vein for infusion of insulin and glucose. A second catheter will be placed retrograde in a dorsal vein of the contra-lateral hand for blood withdrawal. The hand will be placed in a heating box or pad at 70°C for arterialization of venous blood. A primed infusion of regular insulin (120 mU/min/m²) will be initiated and continued for approximately 2 hours. Beginning 20 minutes prior to the start of the insulin infusion, arterialized venous blood glucose will be measured at 5 minute intervals via a Hemocue analyzer. Following initiation of insulin infusion, blood glucose will be allowed to fall to 50 mg/dL and then maintained at this level using a variable infusion of exogenous dextrose (20% solution). Our goal is to achieve steady-state (blood glucose stabilized at 50 mg/dL) within the first 45 minutes following the start of insulin infusion, thus participants blood glucose will be maintained at this level for approximately 75 minutes.

In addition to the Hemocue glucose measurements, blood will be collected every 15 minutes starting 15 minutes prior to insulin infusion, for determination of glucose, insulin levels, and counterregulatory hormone levels in circulation (10 blood draws total). Potassium levels will be measured at three of these time points: -15, 60, and 120 minutes (relative to the start of the insulin infusion). See Table 2 for an overview of the timing of blood draws and measurements.

Following discontinuation of the insulin, blood glucose will be normalized to baseline levels with the 20% dextrose infusion. The participant's blood glucose will continued to be monitored every 15 minutes via Hemocue analyzer for approximately 90 minutes after discontinuation of insulin infusion to ensure baseline levels of blood glucose are achieved and maintained.

If potassium levels are below 3.8 mmol/l at any of the three measurements (-15, 60, or 120 minutes) a potassium infusion of 10 mEq/hr will be initiated and continued for the remainder of the procedure. In the event that a potassium infusion is initiated, potassium levels may be measured again following discontinuation of insulin infusion, i.e. during the 90 minute recovery period when blood glucose levels will be restored and maintained at baseline levels (120-210 minutes relative to the start of the insulin infusion).

Table 2. Schedule of measurements during clamp

Time relative to insulin infusion	Measurement							
	Glucose, insulin, and Potassium				Counterregulatory Hormones			
	Glucose (Hemocue)	Glucose (Clinic Chem.)	Insulin	Potassium	Epinephrine	Norepinephrine	Glucagon	Cortisol
-20 minutes	x							
-15 minutes	x	x	x	x	x	x	x	x
-10 minutes	x							
-5 minutes	x							
0 minutes	x	x	x		x	x	x	x
5 minutes	x							
10 minutes	x							
15 minutes	x	x	x		x	x	x	x
20 minutes	x							
25 minutes	x							
30 minutes	x	x	x		x	x	x	x
35 minutes	x							
40 minutes	x							
45 minutes	x	x	x		x	x	x	x
50 minutes	x							
55 minutes	x							
60 minutes	x	x	x	x	x	x	x	x
65 minutes	x							
70 minutes	x							
75 minutes	x	x	x		x	x	x	x
80 minutes	x							
85 minutes	x							
90 minutes	x	x	x		x	x	x	x
95 minutes	x							
100 minutes	x							
105 minutes	x	x	x		x	x	x	x
110 minutes	x							
115 minutes	x							
120 minutes	x	x	x	x	x	x	x	x
135 minutes*	x							
150 minutes*	x							
165 minutes*	x							
180 minutes*	x							
195 minutes*	x							
210 minutes*	x							
Total per Clamp:	35	10	10	3	10	10	10	10

*Denotes measurements during the recovery period

- Questionnaire: Participants will complete a Screening Health Questionnaire (to assess general health) at the screening visit.
- Vital Signs: Vital signs will be collected according to PBRC standard operating procedures. Seated vital signs (blood pressure and heart rate) will be measured after a 5 minute rest.

Power analysis

Given that this is a method development study and we are not comparing across groups or individual participants, a power analysis was not performed.

Data and Specimen Management

Study data collected and entered into the Pennington Biomedical Database is handled only by individuals with appropriate HIPAA compliance and Good Clinical Practice training. Participant charts and hard copy data are stored in locked offices with restricted access. Electronic data has exclusive restricted access granted by the Research Computing Group and/or the PI. For quality control, data and charts will be audited for completeness and accuracy (when possible).

Study data and specimens will be stored indefinitely at Pennington Biomedical in the Clinical Chemistry and [name] Laboratories. Data will be stored with the participant's de-identified ID number. Specimens will be labeled with the participant's de-identified ID number and date of collection. Data and specimens are accessible by the PI, his staff and designated Clinical Chemistry staff in buildings with restricted access

Data analyses: The purpose of this study is to demonstrate proficiency with the hypoglycemic clamp procedure. This will involve demonstrating the ability to achieve and maintain a steady-state blood glucose of approximately 50 mg/dL for approximately 75 minutes and that we are able to measure the known increases in counterregulatory hormone levels associated with exposure to hypoglycemia. This will be indicated by an increase in all four hormones during the steady-state period of the procedure relative to baseline.

Provisions to Monitor the Data to Ensure the Safety of Subjects

We will use the definitions of *Adverse Events*, *Serious Adverse Events*, and *Unanticipated Problems Involving Risks to Subjects or Others* below. Events will be recorded from the participant during their inpatient stay by experienced staff trained in the ascertainment of adverse events from research participants. For each sign, symptom or adverse event, the following information will be recorded:

- A brief descriptor of the adverse event
- Date of onset and date of resolution
- Frequency (single / intermittent)
- Maximum intensity (mild / moderate / severe)
- Outcome (resolved / resolved with sequelae / not resolved)

- Action taken with respect to study drug/intervention (none / dose reduced / temporarily interrupted/ permanently discontinued/ intervention).
- Withdrawal (yes / no)
- Relationship to study drug/intervention
- Whether the AE was “serious” or not (as defined below)

The Pennington Biomedical Research Center’s Human Research Protections Program’s definitions for adverse event, serious adverse event, and unanticipated problem involving risks to subjects or others (Policy 8) will be applied in this study and are as follows:

- An **adverse event** is any untoward physical or psychological occurrence in a human subject participating in research, including any abnormal sign (e.g., abnormal physical exam or laboratory finding, symptoms or disease associated with the research or the use of a medical investigational test article), symptom, or disease, temporally associated with the subject’s participation in the research. An adverse event does not necessarily have to have a causal relationship with the research, or any risk associated with the research or the research intervention, or the assessment.
- A **serious adverse event** is defined as an adverse event that is fatal or life-threatening, permanently disabling, requires or prolongs hospitalization or results in significant disability, congenital anomaly or birth defect.
- An **unanticipated problem involving risks to subjects or others** is defined as any incident, experience, outcome or new information where all three elements exist:
 - Is unexpected;
 - Is related or possibly related to participation in the research, and
 - Indicates that subjects or others are at a greater risk of harm (including physical, psychological, economic, or social harm) than was previously known or recognized.

While federal guidelines do not require the reporting of adverse events to the IRB, unanticipated problems involving risks to subjects or others will be reported to the IRB within 10 working days of ascertainment of the event per HRPP guidelines.

Upon completion of each participant, participant’s anthropometric and adverse event data will be reviewed by the Medical Investigator with the Principal Investigator to evaluate the data collected regarding both harms and benefits to determine whether subjects remain safe. When incidental findings on imaging studies or out of range values on lab tests are obtained by study personnel, the participant will be notified and a copy of the report sent to his physician. For lab tests, this pertains only to those tests for which results are obtained in real-time.

Withdrawal of Subjects

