These can be reversed within minutes by stopping the insulin infusion and by raising the blood sugar via increased rate of dextrose infusion. To be certain that the participant's blood sugar level does not drop less than 30 mg/dL, blood glucose will be checked every 5 minutes and adjust as needed. If blood sugar drops too low, seizures or abnormalities in heart rhythm can occur. With careful monitoring, it is very unlikely that the participant's blood glucose will drop to

unsafe levels. In the unlikely event that a participant's blood glucose does drop to less than 30 mg/dL, dextrose will be administered immediately.

The risks of hypoglycemia will be minimized by monitoring the blood glucose every 5 minutes and providing dextrose as needed to achieve the target level of blood glucose. Subjects will also wear a pulse oximeter during the study so we can monitor their heart rate. If we become unable to monitor the glucose during the study or if the participant develops a serious arrhythmia (as defined by the medical staff present), or if blood glucose drops to less than 30 mg/dL, the study will be stopped and dextrose will be given to normalize the blood glucose levels. Medical staff will be present throughout the procedure to monitor the patient. The study will be stopped if the medical staff feels that it is no longer safe for the participant to continue. With careful monitoring, it is very unlikely that a participant's blood glucose will drop to less than 30 mg/dL. If blood glucose drops to less than 35 mg/dL, blood samples will be collected every 3 minutes.

Additional countermeasures to hypoglycemia will also be utilized as necessary.

- **IV Procedure:** There is a possibility of pain, bruising, or infection at the site of the needle insertion for the IV line. Trained personnel also minimize this risk.
- **Questionnaire:** There is a possibility that participants will be uncomfortable answering certain questions. Participants will be told that they may choose to skip any questions.

Potential Benefits to Subjects

There is no direct benefit to participants.

Sharing of Results with Subjects

Results will not be shared with participants.

Setting

This study will be conducted at Pennington Biomedical Research Center in the Outpatient Unit and Inpatient Unit.

Resources Available

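### Blood glucose checks widen from every 5 to every 15 minutes when insulin stops, not when glucose has recovered, so none is scheduled between 120 and 135 minutes

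*Protocol*

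**What the plan says.** Under Study Procedure Descriptions, the clamp item sets the dense schedule: from 20 minutes before insulin, "arterialized venous blood glucose will be measured at 5 minute intervals via a Hemocue analyzer". Glucose is to reach 50 mg/dL within about 45 minutes and be held there for about 75 minutes, that is, until insulin stops at 120 minutes.

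The same item then describes recovery: "Following discontinuation of the insulin, blood glucose will be normalized to baseline levels with the 20% dextrose infusion". No dextrose rate or time target is given for this step, nor a rule for when baseline counts as reached. For monitoring it says: "blood glucose will continued to be monitored every 15 minutes via Hemocue analyzer for approximately 90 minutes after discontinuation of insulin infusion". Table 2 agrees. After the 120-minute row, the next Hemocue row is 135 minutes, then every 15 minutes to 210.

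Risks to Subjects says that the risk of hypoglycemia is reduced by "monitoring the blood glucose every 5 minutes and providing dextrose as needed to achieve the target level of blood glucose", without saying which part of the procedure this covers. It adds an escalation rule: "If blood glucose drops to less than 35 mg/dL, blood samples will be collected every 3 minutes".

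**The concern.** The interval triples because insulin has stopped, not because glucose has been shown to recover. At 120 minutes glucose is, by design, at its lowest planned level. The task also changes, from holding a fixed target to moving glucose to a new level with the same 20% dextrose. For that step the schedule gives one third of the readings, and none in the first 15 minutes. A slow response or an overshoot in that window would not be seen by any scheduled blood reading, and the dextrose rate would be set without one.

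This matters more here than at a site with a settled procedure. Background says of this site that "experience performing the hypoglycemic clamp procedure is lacking", and Objectives says that the study is to "develop an institutional MOP for the hypoglycemic clamp which can be used to safely implement this technique in future studies". A recovery schedule fixed by the clock could be carried into later studies through that manual.

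**Working it through.** **Inputs**
- Hemocue every 5 minutes from -20 to 120 minutes (clamp description; Table 2).
- Hemocue every 15 minutes from 135 to 210 minutes (recovery text; Table 2).
- Glucose about 50 mg/dL from about 45 to 120 minutes (clamp description).
- Printed Hemocue total in Table 2: 35 per clamp.
- Goal of 3 completers, up to 8 enrolled (Study Participants).

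**The protocol's own total**
- -20 to 120 minutes: (120 + 20)/5 + 1 = 29.
- 135 to 210 minutes: (210 - 135)/15 + 1 = 6.
- Sum: 29 + 6 = 35, as printed.

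The total matches only the 15-minute recovery interval. Five-minute checks throughout recovery would give 29 + 90/5 = 29 + 18 = 47. So the 15-minute step is intended and is not a misreading of the table.

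**The gap**
- Scheduled blood readings strictly between 120 and 135 minutes: 0.
- Scheduled in the first 15 minutes after insulin stops: 1 (at 135). With 5-minute checks: 3 (at 125, 130 and 135).
- The time at which glucose regains baseline is located to within 15 minutes now, and to within 5 minutes with the change.

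**Extra readings if 5-minute checks continue until baseline is confirmed**

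| 5-minute checks run to | Added time points (minutes) | Extra | New total |
|---|---|---|---|
| 135 | 125, 130 | 2 | 37 |
| 150 | also 140, 145 | 4 | 39 |
| 165 | also 155, 160 | 6 | 41 |
| 180 | also 170, 175 | 8 | 43 |
| 210 | all remaining 5-minute points | 18 - 6 = 12 | 47 |

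The floor is 2. Two consecutive recovery readings cannot be complete before 130 minutes, and confirmation at 130 or at 135 needs the same two added points.

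- Three completers: 3 x 2 = 6 to 3 x 12 = 36 extra readings, against 3 x 35 = 105 planned.
- If all 8 enrolled were clamped: 8 x 2 = 16 to 8 x 12 = 96.

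**How fast glucose must rise for each confirmation time.** The protocol gives no expected fasting level, so 80 to 100 mg/dL is assumed. With a tolerance of 10 mg/dL below baseline (proposed under the fix), the rise needed from 50 is 80 - 10 - 50 = 20 to 100 - 10 - 50 = 40 mg/dL.
- Confirmed at 130 (in range by 125): 20/5 to 40/5 = 4 to 8 mg/dL per minute.
- Confirmed at 135 (in range by 130): 20/10 to 40/10 = 2 to 4 mg/dL per minute.
- Confirmed at 150 (in range by 145): 20/25 to 40/25 = 0.8 to 1.6 mg/dL per minute.

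The protocol gives no dextrose rate for recovery, so it does not show which of these to expect. The cost is therefore stated as a range.

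**The case against.** The strongest reply is that nothing here is wrong. The text and Table 2 agree, and the recovery checks have a stated purpose: to see that baseline is reached and kept. Insulin is off and dextrose is running. The 4-hour procedure in Study Visit includes the 90-minute recovery, so the commitment in Risks to Subjects to keep medical staff present covers this window. Heart rate is monitored by oximeter, staff may stop the procedure, and further countermeasures are allowed as needed. Background also says that the site knows the euglycemic clamp well, regards the two procedures as very similar, and consulted an experienced center. The proficiency criteria under Data analyses concern the plateau and the hormone rises, not the speed of recovery.

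Much of this stands. It limits the point to an improvement in the schedule, and it rules out several stronger readings that a reader might infer:

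- **That the protocol contradicts itself.** The 5-minute statement in Risks to Subjects has no end point, but it can be read as covering only the insulin infusion. The specific recovery text and Table 2 probably govern. This calls for a clarifying phrase and does not prove an inconsistency.
- **That glucose is not recorded at all from 120 to 135 minutes.** The CGM records every 5 minutes and stays on until after lunch. The gap is in blood readings. The CGM does not fill it, because it measures interstitial glucose, is calibrated from clamp values, has no stated safety role, and its accuracy in hypoglycemia is something the study sets out to learn.
- **That the low-glucose rules fail.** The 35 mg/dL rule does need a reading to trigger it, but glucose would have to fall a further 50 - 35 = 15 mg/dL after two steps meant to raise it. The 30 mg/dL rescue consists of stopping the procedure and giving dextrose, which is already under way. Neither supports a claim of likely harm.
- **That the reversal claim is broken.** The statement "These can be reversed within minutes by stopping the insulin infusion and by raising the blood sugar via increased rate of dextrose infusion" refers to symptoms, which attending staff can observe. It sets no time scale for measured glucose.

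What does not stand is that these safeguards replace a reading. Presence and oximetry do not measure glucose. Unscheduled readings are possible, but the schedule does not call for them.

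**Conclusion.** The point holds as a low-cost improvement to a rule that the protocol states explicitly. The Hemocue interval goes from 5 to 15 minutes at 120 minutes because insulin stops, while glucose is planned at about 50 mg/dL and normalization is only beginning. No blood reading is scheduled for the next 15 minutes. The gain is that the rise is confirmed, and the dextrose rate guided, by two further readings in that window. The return to baseline is also located to within 5 rather than 15 minutes, which is useful for the manual although it is not one of the stated proficiency criteria.

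Glucose is expected to rise, no probability of harm is claimed, and no endpoint or analysis changes. The reading counts rest only on Table 2. The required rates of rise rest on an assumed fasting baseline of 80 to 100 mg/dL, and the conclusion does not depend on them.

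**What to change.** Amend the recovery text and Table 2 so that Hemocue checks continue every 5 minutes after 120 minutes until two consecutive readings are back at baseline within a stated tolerance, then every 15 minutes to 210 minutes as now. A workable definition is no more than 10 mg/dL below the mean of the participant's own five readings from -20 to 0 minutes. Both the two-reading rule and the 10 mg/dL tolerance are proposals; the investigators may prefer other values, but should state them. The Hemocue total in Table 2 then becomes 37 to 47 instead of a fixed 35.

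In Risks to Subjects, state that the 5-minute checks and the 35 mg/dL rule apply until baseline has been confirmed in this way.

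The cost is a wording change plus 2 extra readings per clamp if baseline is confirmed by 135 minutes, 4 if by 150, and at most 12, with more in total if more than three participants are clamped. The sampling line, analyzer and staff are already in place. Some additional blood is drawn; the protocol gives no volume per Hemocue sample, so the amount cannot be computed from it. The investigators should check it against the stated approximate 120 mL for the clamp.

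### Does measuring the primary endpoint on two glucose analyzers, without naming the deciding one, make the 50 mg/dL criterion nearly impossible to fail?

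*Protocol*

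**What the plan says.** Under Study Endpoints the primary endpoint is "Blood glucose levels", with no analyzer, summary or time window. CGM glucose is listed separately as secondary, so it is not a candidate for the primary.

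The clamp description provides two blood glucose series. In the first, "arterialized venous blood glucose will be measured at 5 minute intervals via a Hemocue analyzer". The second is laboratory glucose: "In addition to the Hemocue glucose measurements, blood will be collected every 15 minutes starting 15 minutes prior to insulin infusion, for determination of glucose". Table 2 carries it in its own column, "Glucose (Clinic Chem.".

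On control, the clamp description says that "blood glucose will be allowed to fall to 50 mg/dL and then maintained at this level using a variable infusion of exogenous dextrose (20% solution"). Risks to Subjects describes "monitoring the blood glucose every 5 minutes and providing dextrose as needed to achieve the target level of blood glucose". Only the Hemocue is scheduled that often up to 120 minutes.

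The success criterion, in the Data analyses paragraph of Data and Specimen Management, is "demonstrating the ability to achieve and maintain a steady-state blood glucose of approximately 50 mg/dL for approximately 75 minutes", together with a rise from baseline in all four counterregulatory hormones. Objectives adds that the time course of each endpoint is examined subject by subject and compared with published clamps, and that no hypothesis is tested.

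**The concern.** Two instruments measure one endpoint, and they do not have the same standing. If dextrose is adjusted until the Hemocue shows 50, a Hemocue plateau near 50 is partly a statement that staff followed the meter. A constant meter bias leaves no trace in that series. Only the laboratory values could expose it, and the success criterion does not mention them.

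The criterion also has no tolerance. Judged on a mean, a plateau alternating between 40 and 60 mg/dL would average exactly 50.

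If both points held, the primary result would be close to assured. An offset in the meter would then pass unnoticed into the institutional procedure that this study exists to produce, and from there into later studies.

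**Working it through.** **1. Reproduce the schedule in Table 2.**
- Hemocue: 4 readings (-20 to -5 min, every 5) + 25 (0 to 120 min, every 5) + 6 (135 to 210 min, every 15) = 35. The table states 35.
- Laboratory: -15 to 120 min, every 15, gives 10. The table states 10.
- Plateau: 120 - 45 = 75 minutes, as stated. It holds (75/5) + 1 = 16 Hemocue values and (75/15) + 1 = 6 laboratory values.
- Every laboratory time is also a Hemocue time, so there are 10 pairs per clamp, 6 of them on the plateau. With 3 completers that is 30 pairs, 18 on the plateau.

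**2. Size of a hidden bias.** The documents give no meter bias, so 5% to 15% is an assumption, and so is taking the laboratory value as true glucose. With the Hemocue held at 50, laboratory glucose = 50/(1 + bias):

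| Assumed Hemocue bias | Laboratory glucose (mg/dL) |
|---|---|
| -15% | 58.8 |
| -10% | 55.6 |
| -5% | 52.6 |
| +5% | 47.6 |
| +10% | 45.5 |
| +15% | 43.5 |

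At +10% the plateau pairs would differ by 50 - 45.5 = 4.5 mg/dL on average, in the same direction in every participant. The planned data show that difference directly.

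**3. Can the Hemocue criterion fail?** A simulation of 40,000 clamps used 16 Hemocue values centred on 50, with first-order autoregressive control error (correlation 0.6). The laboratory values were every third reading divided by (1 + bias), with no added assay error. Control CV, correlation and pass rules are all assumptions.

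| Assumed pass rule | Control CV | Hemocue passes |
|---|---|---|
| Mean within 50 ± 10 | 5% | about 100% |
| Mean within 50 ± 5 | 10% | about 97% |
| Every value within 50 ± 10 | 10% | about 56% |
| Every value within 50 ± 5 | 5% | about 56% |
| Every value within 50 ± 10 | 15% | about 9% |
| Every value within 50 ± 5 | 10% | about 1% |

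The Hemocue verdict ignores meter bias but responds strongly to quality of control. These rates already assume that staff are on target on average from 45 minutes; late arrival would lower them.

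**4. Does the choice of analyzer matter?** Under the rule of a mean within 50 ± 5 and a control CV of 10%, the Hemocue passes about 97% of clamps whatever its bias. The laboratory passes about 96% with no bias, 58% at +10% and 24% at +15%. The two series could therefore disagree, but only if a bias of that size exists.

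**5. The 40/60 example.** Alternating values give mean (40 + 60)/2 = 50 and SD 10 (divisor n), so CV = 10/50 = 20%. Taking every third value, as the laboratory schedule does, still alternates: three at 40 and three at 60, mean 50. The example therefore faults a mean rule on either analyzer, and the protocol contains no such rule. The clamp description equates steady state with glucose being stabilized at 50, and the subject-level time course would show the swing.

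**The case for a change.** The best case for a change is that the choice of instrument is part of the endpoint's definition, not an analysis detail to be left to a SAP. The protocol states its own success criterion and still leaves the instrument open. The hormones get a concrete direction of change, while the primary endpoint gets only an approximate level. The CGM is calibrated to blood glucose from the clamp, again without naming the analyzer, so the ambiguity reaches the CGM-accuracy data as well. Naming the analyzer would cost only wording, since every sample is already planned.

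Part of this stands. The deciding series is not named, no tolerance is given, and a Hemocue-only verdict would be blind to meter bias.

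The stronger claims do not stand. Fifty is a target, and Background says the institution lacks experience with this procedure. Whether staff can reach and hold the level is the proficiency under test, and the steering series is a fair measure of that. Risks to Subjects foresees readings below 35 and stopping below 30 mg/dL, so the protocol itself expects that control may miss. The hormone requirement can fail whichever glucose analyzer is used. Nothing excludes the laboratory values from the primary endpoint, so a bias stays hidden only if planned data are ignored.

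The obvious remedy is also not a clear gain. Making the laboratory series primary replaces 16 values with 6 and gives up time resolution on whether the level was held, which is half of the criterion. A pass mark such as a mean of 45 to 55 mg/dL with a CV of at most 10% has no basis in the documents.

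**Conclusion.** The concern is right that the analyzer and the tolerance are unwritten, and wrong that the criterion can hardly fail. Followed as written, the plan yields both series for every completer, examined over time in each subject: the Hemocue values show how steadily the level was held, and the paired laboratory values show what level was attained. An analyst would report both, and the 10 differences per clamp would expose a meter offset.

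The possible discrepancy is about 2 to 9 mg/dL at the plateau (50 against 47.6 to 43.5, or against 52.6 to 58.8). It rests wholly on an assumed bias of 5% to 15% and on the laboratory value being correct. The study has no hypothesis test, no power calculation and a goal of 3 completers, so no error rate is at stake. Numerical limits are commonly set in a SAP or manual of procedures, and neither is shown here. This is a gap that analysts fill sensibly, and no change to the plan is needed.
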